## **METHODS: INTERVENTION ALLOCATION**

### **16-17 Randomization**

Trained staff in the catheter laboratory will use a web-based randomization tool, available 24h/24h at any of the enrolling sites, to immediately randomize the patient after the index coronary angiography revealing non obstructive CAD, to “precision medicine approach” versus “standard approach” (open label approach: both patients and physicians will know the allocated treatment arm).

## **METHODS: DATA COLLECTION, MANAGEMENT AND ANALYSIS**

**18. Data collection:** Data collection will be carried out through an electronic CRF (eCRF). The investigator or an authorized member of the investigation team must sign all completed eCRFs with a digital signature (a password will be provided by the data management center at the start of the study). The management of clinical data will be carried out in accordance with the data cleaning procedures, both for the data recorded in the eCRFs and from other sources. Appropriate computerized software will be used to verify the accuracy of the database. Investigators will be asked for incomplete, inconsistent or missing data.

**Source Documents (SDs):** Investigators have to maintain information in the patient's medical record that corroborates the data collected in the eCRF. To meet these demands, the following is a list of information that must be recorded and shown to monitors and regulatory inspectors as needed: Clinical history / physical condition of the participant before inclusion in the study with sufficient detail to verify the inclusion and exclusion criteria; clinical notes dated and signed on the day of entry into the study, protocol number, clinical site, number assigned to the patient and a declaration certifying the signature of the informed consent; record of abnormal laboratory tests; reported adverse events and their resolution; including supporting documents such as discharge sheet, catheterization reports, ECG, echocardiography and CMR reports; laboratory results; condition of the patient upon completion or withdrawal from the study.

**Case Report Form:** All requested data will be carefully recorded by authorized personnel documented in the Authorized signature log in the eCRF.

**19. Confidentiality:** All data and information collected during this study concerning the participant must adhere to the privacy protection standards, based on the application of the Italian laws on the

confidentiality of the participating subjects and the European General Data Protection Regulation (GDPR). All data used for the analysis and the study summary will be anonymous and without specific references to the names of participants. Access to the subjects' personal files will be limited to authorized personnel, investigators and research staff. Authorized personnel from regulatory agencies have the right to inspect and copy all records relevant to this study, but every effort must be made to remove the subjects' personal data.

**Record Storing:** All information in the eCRF, study records, reports and SDs that support the eCRF must be kept in the files of the investigator responsible in accordance with national requirements, and will be stored further in accordance with national and international guidelines as described in the Investigator Site Agreement. This documentation must be accessible if required by international regulatory authorities. The documentation and data collected must be kept for at least 15 years after the completion or suspension of the trial itself.

## **20. Statistical analysis**

The study population will comprise participants who had provided informed consent. There will be no interim analyses, and the trial enrolment will be considered complete after the pre-specified recruitment target was met. Data will be reported as mean  $\pm$  SD, median (25th, 75th percentile), or frequency and percentage. Continuous outcome measures recorded at baseline and 6 months will be compared between randomized groups using a mixed effects linear regression model, including a random effect for patients, and fixed effects for time point (baseline or follow-up), randomized group, and their interaction. The baseline-adjusted intervention effect will be estimated as the interaction term from this model. Categorical outcomes will be compared between randomized groups using Fisher exact tests with additional calculation of relative risk estimation of effect size. We will perform 2-tailed analysis and considered a p value  $\leq 0.05$  to be significant. Statistical analyses will be performed using SPSS program.

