## **12. Outcomes of interests:**

Primary endpoints:

- Angina status and quality of life (evaluated using the Seattle Angina Questionnaire [SAQ]) at 1-year follow-up in patients with MINOCA.

[figure not shown]
\* To reduce the risk of detection and performance bias, a team of 2 cardiologists blinded to group allocation and belonging to an external cardiology unit will submit and collate the questionnaires from study participants.

Secondary endpoints:

- Rates of major adverse cardiovascular events (MACE; composite of all-cause mortality; re-hospitalization for myocardial infarction, stroke or heart failure; repeated coronary angiography) at 1-year follow-up in MINOCA patients.
- Healthcare primary and secondary related-costs (including costs for tests, procedures and outpatient visits or medicines) and socioeconomic burden of MINOCA patients.
- Ability of different circulating biomarkers (ET-1, NPY, CRP, sCD40L and miRNA [miR-16, miR-26a, miR-145, miR-222, miR-155-5p, miR-483-5p and miR-451]) as diagnostic biomarker and stratification tool for specific causes of MINOCA.
- Ability of CMR in evaluating different mechanisms of MINOCA and their prognostic value.

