## Study timeline

# Study Timeline

### *T 0 (index hospitalization for MINOCA):*

During the index hospitalization the study investigators, after a careful evaluation of the inclusion and exclusion criteria of the patients, will collect:

- Anagraphic data
- Personal information: weight, height, BMI
- Vital parameters (blood pressure, heart rate, oxygen saturation)
- Therapy at admission and at discharge (concomitant medications included)
- Cardiovascular risk factors: family history of early coronary artery disease (first degree relative with a history of myocardial infarction <60 years), diabetes mellitus [fasting blood glucose >126 mg/dL or treated diabetes mellitus (intake of a diabetic diet or oral hypoglycaemic agents), according to the American Diabetes Association (ADA) criteria], hypercholesterolemia (total cholesterol >200 mg/dL or treated hypercholesterolemia), smoking (current), and hypertension (systolic blood pressure >140 mmHg and/or diastolic blood pressure >90 mmHg or treated hypertension).

- Relevant comorbidities: anaemia, chronic kidney disease, atrial fibrillation, history of stroke/TIA, peripheral vascular disease
- ECG features (ST segment elevation/depression or T wave inversions, atrioventricular blocks, arrhythmias)
- Trans-thoracic color-Doppler echocardiography (chamber volumes, systolic and diastolic function)
- Data on coronary angiography and ventriculography (presence/absence of non-obstructive CAD, micro vs epicardial coronary spasm, “hazy” angiographic images, TIMI flow, LVEDP)
- Laboratory data (creatinine, full blood count, Troponin I peak, CK-MB peak, NT-proBNP, CRP)

For patients randomized to “*precision medicine approach*”:

- OCT (if coronary plaque rupture/erosion is suspected) at the time of coronary angiography in the cath-lab.
- Acetylcholine provocative test (to assess the presence of coronary vasospasm) at the time of coronary angiography in the cath-lab.
- TE-Echo and/or CE-Echo (if distal/microvascular embolization is suspected) during the hospitalization at the echo laboratory
- CMR with contrast media: anatomical and morphological data
- Blood sampling for circulating biomarkers and miRNA expression profile at the time or within the 12 hours from coronary angiography. Blood sampling will be processed and analysed in the research laboratory of the Department of Cardiovascular Science. Biological aliquots will be preserved at XBiogem Biobank at Fondazione Policlinico Universitario A. Gemelli IRCCS, Rome.

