***T2\_ Follow-up phone interview at 6 months (180 +/- 5 gg)***

- Collection of MACE at follow-up
- Collection of ongoing medical therapy
- Registration of adverse events

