***T4\_ Follow-up clinical visit at 12 months (365 +/- 5 gg)***

- Personal information: weight, height, BMI
- Collection of ongoing medical therapy
- Compilation of SAQ score
- Collection of MACE at follow-up
- Registration of adverse events

Study Assessment	Screening and randomization	Follow-up phone interview_ T1 (3 months)	Follow-up phone interview_ T2 (6 months)	Follow-up phone interview_ T3 (9 months)	Visit of End of Follow-up (12 months)
Days	0	90 +/- 5 gg	180 +/- 5 gg	270 +/- 5 gg	365 +/- 5 gg
Weeks	0	12	24	36	52

Informed consent	X				
Inclusion criteria	X				
Anagraphic data	X				
Personal information (weight, height,BMI)	X				X
Clinical history	X				
Clinical examination	X				
Vital signs	X				
Ongoing medical therapy (concomitant medications included)	X	X	X	X	X
Patients assigned to "Standard approach"	X				
ECG features	X				
Transthoracic Echocardiography	X				
Coronary angiography and ventriculography	X				
CMR with contrast media (if clinically indicated)	X				
Laboratory data (creatinine, full blood count, Troponin I peak, CK-MB peak, NTproBNP, CRP)	X				
Patients assigned to "Precision-medicine approach"					
OCT (if coronary plaque rupture/erosion is suspected)	X				
	X				

Acetylcholine provocative test (to assess the presence of coronary vasospasm)					
TE-Echo and/or CE-Echo (if distal/microvascular embolization is suspected)	X				
CMR with contrast media (if clinically indicated)	X				
Blood sampling for circulating biomarkers and miRNA expression profile	X				
Collection of MACE	X	X	X	X	X
Adverse events	X	X	X	X	X
SAQ score					X

SAQ score:

1. The following is a list of activities that people often do during the week. Although for some people with several medical problems it is difficult to determine what it is that limits them, please go over the activities listed below and indicate how much limitation you have had **due to chest pain, chest tightness, or angina over the past 4 weeks.**

Place an x in one box on each line.

Activity	Severely Limited	Moderately Limited	Somewhat Limited	A Little Limited	Not Limited	Limited, or did not do for other reasons
Dressing yourself						

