### *Definition of the MACE*

MACE analysis includes:

- All cause death:
  - Cardiac death (in which a direct cause attributable to cardiac disease is present);
  - Sudden cardiac death (in which cardiac death occurred out of the hospital and suddenly; or in the hospital due to ventricular arrhythmias unrelated to other concomitant cardiac conditions);
  - Non-cardiac death (in which the event of death is considered not to be a direct consequence of cardiac disease);
- Hospitalization in which the main diagnosis is myocardial infarction, stroke or heart failure;
- Repeated coronary angiography.

The analysis will consider time to first event and time to each event.

Safety parameters will include data deriving from history and physical examination performed at each visit, laboratory data and results of functional and imaging tests. To enhance detection of adverse events between visits, all patients will be encouraged to contact the research team at any time with concerns or any perceived changes in their healthcare status.

**14. Sample size calculation:** Sample size calculation for the primary endpoint: to detect a mean group difference of change in SAQ score of 9 U, we calculated that a sample size of 70 patients per group (140 patients total) gave 80% power to detect a between-group difference in SAQ. This

calculation assumed a 2-tailed 5% significance level. This projected calculation assumed an SD of 19 U and was consistent with previous studies (see landmark CorMicA trial). However, we extended the sample size at 180 patients to avoid any reduction of statistical power due to patients lost at follow-up or due to poor compliance to medical therapy.

**15. Timeline:** At 36 months all patients will be enrolled and will have completed the follow-up. The study will be considered ended after the date of last patient last visit (LPLV). Blood samples will be analysed for assessment of circulating biomarkers and miRNA to detect associations with specific mechanisms underlying MINOCA, for stratification of prognosis and to evaluate response to medical therapy. Furthermore, CMR sequences will be analysed to detect functional and structural characteristics associated with specific mechanisms underlying MINOCA and with for stratification of prognosis.

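### The primary endpoint, SAQ at 1 year, is scheduled only once, at 12 months, so the baseline-to-6-month interaction that Section 20 takes as the treatment effect cannot be computed for it

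*Combined protocol and SAP*

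**What the plan says.** The primary endpoint in Section 12 is "Angina status and quality of life (evaluated using the Seattle Angina Questionnaire [SAQ]) at 1-year follow-up in patients with MINOCA".

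Section 14 sizes the trial "to detect a mean group difference of change in SAQ score of 9 U", with 70 patients per group for 80% power at a two-sided 5% level, raised to 180 in total to cover losses and poor compliance. On the variability it says: "This projected calculation assumed an SD of 19 U and was consistent with previous studies". It does not say whether 19 U is the SD of a change or of a single score.

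Section 20 does not mention SAQ or name a primary analysis. For continuous outcomes it says: "Continuous outcome measures recorded at baseline and 6 months will be compared between randomized groups using a mixed effects linear regression model". The model has a random patient effect and fixed effects for time (two levels), group and their product. It continues: "The baseline-adjusted intervention effect will be estimated as the interaction term from this model". The only other comparison it names is Fisher's exact test, for categorical outcomes.

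On data collection, the T0 list begins "During the index hospitalization the study investigators, after a careful evaluation of the inclusion and exclusion criteria of the patients, will collect" and contains no SAQ. The contact described as "Follow-up phone interview at 6 months (180 +/- 5 gg" days) covers MACE, therapy and adverse events only, as do those at 3 and 9 months. "Compilation of SAQ score" appears only under T4, the 12-month visit. The SAQ row of the assessment table has one mark, in the 12-month column.

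**The concern.** The endpoint, the sample size, the model and the visit schedule cannot all be followed. Neither time point named in the model has a scheduled SAQ value, and the sample size rests on a change for which no starting value is collected.

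This matters more than an ordinary wording gap for three reasons.

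- It concerns the primary endpoint, which is patient-reported in an open-label trial. If the analysis is undefined, someone must choose it later, possibly with results in view.
- The SAQ asks mainly about the preceding 4 weeks. A baseline not taken around the index admission cannot be recovered for that patient.
- If the team falls back on 12-month scores alone, the stated power carries over only if 19 U is the SD of a single score.

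**Working it through.** **Planned size.** Inputs from Section 14: difference 9 U, SD 19 U, two-sided 5%, 80% power, 1:1 allocation.

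n per arm = 2 × (1.960 + 0.842)² × 19² / 9² = 69.96, so 70 per arm and 140 in total. The plan's figure reproduces. Power by the two-sided t-test is 79.5% at 70 per arm and 88.5% at 90 per arm (all 180 evaluable). The 70-per-arm case means all 40 extra patients are lost, 40/180 = 22%.

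**Can the stated effect be estimated?** The fixed part of the model has four terms: intercept, time, group and time × group.

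- SAQ at one time point only: the design matrix has rank 2 of 4. Time cannot be separated from the intercept, nor time × group from group. Only a difference in means at that time point can be estimated.
- SAQ at baseline and 12 months: rank 4 of 4, and the interaction can be estimated.

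Reading 6 months as 12 months is therefore not enough. A baseline score is also needed.

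**Power for 9 U when only 12-month scores are compared.** This depends on what 19 U is.

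*If 19 U is the SD of a single score*, power is as above: 79.5% at 70 per arm and 88.5% at 90.

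*If 19 U is the SD of change*, and SDs are equal at both times with correlation r between them, the single-score SD is 19/√(2(1 − r)). The documents give no r, so the range below is an assumption.

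| Assumed r | Single-score SD (U) | Power, 70/arm | Power, 90/arm |
|---|---|---|---|
| 0.3 | 16.06 | 90.9% | 96.2% |
| 0.5 | 19.00 | 79.5% | 88.5% |
| 0.6 | 21.24 | 70.2% | 80.7% |
| 0.7 | 24.53 | 57.8% | 68.7% |

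On this reading the interaction, were baseline available, would have 79.5% or 88.5% at any r. Dropping baseline loses power only when r is above 0.5 and gains power below it. By the t-test, 80% power for 12-month scores alone needs a single-score SD of at most about 18.9 U at 70 per arm or 21.4 U at 90.

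**The reverse case.** If 19 U is the SD of a single score and a baseline is added, then with complete data the interaction is a comparison of mean change, with SD 19√(2(1 − r)). For r = 0.3 to 0.7 this is 22.5 down to 14.7 U, and power is 65.2% to 94.9% at 70 per arm and 76.1% to 98.3% at 90. If baseline enters instead as a covariate, the residual SD is 19√(1 − r²). At r = 0.3 that is 18.1 U, with power of about 83% at 70 per arm and 91% at 90.

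**The case against.** The strongest reply is that a baseline SAQ was plainly intended. Section 14 speaks of change and Section 20 of baseline values, so the schedule may simply have an omission. The T0 list is not exhaustive: the assessment table puts clinical examination, MACE and adverse events at day 0, and the T0 list leaves them out. The figures under the primary endpoint and in the flow chart are not visible in the text available, and one of them could show a baseline SAQ. This lowers certainty about intent. It does not remove the contradiction, because the prose lists and the table both place SAQ at 12 months alone, and sites would work from them.

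A second reply is that Section 20's sentence covers only measures recorded at baseline and 6 months, so strictly it does not reach SAQ. That is fair, but the plan then states no analysis of its primary endpoint at all, which is no better.

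A third is that no definite loss of power has been shown. This stands: the correlation is assumed, and dropping baseline could help or harm. By the normal formula the SD limit at 70 per arm is also 19.0 U, the plan's own figure; 18.9 U comes from the t-test. Section 14 closes by referring to a difference in SAQ without the word change, so it can be read as powering a single-score comparison. The point is that the plan does not say which.

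Finally, a comparison of 12-month scores is valid and needs only rewording. That is accepted. The trial can still answer its question, but the stated analysis cannot be carried out.

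**Conclusion.** The concern holds and must be fixed. As scheduled, 0 of 180 patients have a baseline SAQ, and the effect defined in Section 20 cannot be estimated for the primary endpoint, even with 6 months corrected to 12. The sample size arithmetic is sound.

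The effect on power is uncertain rather than adverse. A 12-month-only comparison has 79.5% to 88.5% power if 19 U is a single-score SD. If 19 U is the SD of change, it has between 58% and 96% across both sample sizes, given an assumed correlation of 0.3 to 0.7 and equal SDs at the two times. The finding about the schedule rests on the visit lists and assessment table; the missing figures could not be checked.

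**What to change.** In Section 20, replace 6 months with 12 months and name 12-month SAQ as the primary analysis, stating which SAQ scale or score is meant. In Section 14, state whether 19 U is the SD of change or of a single score. Then choose one option.

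**Option 1: collect a baseline.** Add SAQ to the T0 list and the assessment table, during the index admission, after consent and before allocation is known where feasible. Keep a baseline-adjusted model. Baseline as a covariate is worth considering, since the interaction can have less power than no baseline at all when the correlation is low. State who administers the baseline questionnaire, because Section 12 assigns the questionnaires to a blinded external team. Since a missed baseline cannot be recovered, this must be in place before enrolment, or the plan must say how patients already enrolled are handled.

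The cost is one 11-item questionnaire (the first item has nine activity rows) and no extra visit. Randomisation immediately after angiography means some patients would complete it knowing their allocation, which could bias the adjustment. Items 5 to 8 concern pills, treatment and explanations for angina and may not apply to a patient not yet treated. The external team may be needed at admission.

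**Option 2: no baseline.** Remove change from Section 14 and the baseline/time model from Section 20, specify a between-arm comparison of 12-month SAQ, and restate the power for a single-score SD. This costs only wording and a recalculation.

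Either change should be made by amendment before any outcome data are examined.

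### The effect that section 20 labels baseline-adjusted is in substance the plain difference in mean change; conditioning on baseline SAQ would be more precise at no extra cost in patients

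*Combined protocol and SAP*

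**What the plan says.** Section 20 gives one method for continuous outcomes: "Continuous outcome measures recorded at baseline and 6 months will be compared between randomized groups" by a mixed linear model, "including a random effect for patients, and fixed effects for time point (baseline or follow-up), randomized group, and their interaction". It then names the estimator: "The baseline-adjusted intervention effect will be estimated as the interaction term from this model". No baseline covariate is listed, and the two arms are not constrained to share a baseline mean.

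Section 14 sizes the trial "to detect a mean group difference of change in SAQ score of 9 U". It adds "This projected calculation assumed an SD of 19 U" without saying whether this is the SD of a change or of a single score. The target is 80% power with 70 patients per group, two-sided 5%, raised to 180 in total to cover losses.

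The primary endpoint in section 12 is "Angina status and quality of life (evaluated using the Seattle Angina Questionnaire [SAQ]) at 1-year follow-up". The visit schedule in section 13 lists the SAQ only at the 12-month visit.

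**The concern.** A reader of section 20 will take baseline-adjusted to mean that the comparison conditions on the baseline score. The model does not do that. Two arms at two times give four cell means, and the model has four fixed parameters, so the interaction can only contrast the two mean changes.

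Subtracting baseline removes the whole chance difference between the arms at baseline, when only the part that carries through to follow-up should be removed. Two things follow. In any one trial the estimate is displaced by the uncorrected part of the imbalance, and the standard error is larger than it needs to be. As this is the only estimator given for continuous outcomes, it would govern the primary SAQ comparison.

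**Working it through.** **Inputs.** From section 14: difference 9 U, SD 19 U, two-sided 5%, 80% power, 70 per group, 180 enrolled. From section 20: the model terms. The correlation r between baseline and follow-up SAQ is given nowhere. It is an assumption, shown at 0.3, 0.5 and 0.7, with equal SD s at both times.

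**1. The plan's own figure.** n per arm = 2(1.960 + 0.842)² × 19² / 9² = 69.96, so 70. This reproduces, with 80.0% power by the normal formula. With the t distribution, 70 per arm gives 79.5%. The t distribution is used for the powers below.

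**2. What the interaction estimates.** The fixed effects reproduce the four cell means. With complete pairs the interaction is (mean change, precision arm) − (mean change, standard arm). Fitting the section 20 model to 75 simulated complete data sets of 70 per arm confirmed this: the two estimates never differed by more than 1e-12.

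The identity is not exact when follow-up is missing. Enrolling 180 for 140 evaluable allows 1 − 140/180 = 22% loss. In one simulated set with 22% of follow-up missing, the interaction was 5.35 (SE 3.09) and the complete-case change difference 5.48 (SE 3.17). These are close, and neither conditions on baseline.

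**3. Sensitivity to chance imbalance.** If the precision arm happens to start d units higher, the expected interaction estimate is the true effect − (1−r)d. At 70 per arm and a single-score SD of 19 U, the standard error of d is 19 × √(2/70) = 3.21 U. A one-standard-error imbalance then shifts the estimate by:
- r = 0.3: 0.7 × 3.21 = 2.25 U
- r = 0.5: 0.5 × 3.21 = 1.61 U
- r = 0.7: 0.3 × 3.21 = 0.96 U

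The shift can go either way and averages zero over randomisations.

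**4. Precision.** Var(change) = 2(1−r)s². Residual variance after conditioning on baseline = (1−r²)s². The ratio is (1−r²)/[2(1−r)] = (1+r)/2, that is 0.65, 0.75 and 0.85. Where 70 per arm is needed for the interaction, ANCOVA needs 70 × 0.65 = 45.5, 70 × 0.75 = 52.5 and 70 × 0.85 = 59.5, so 46, 53 and 60. Since 2(1−r) exceeds 1 when r is below 0.5, the change contrast is then less precise even than ignoring baseline.

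**5. Power at 70 per arm for 9 U.**

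If 19 U is the SD of change, the ANCOVA residual SD is 19 × √((1+r)/2):

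| r | Interaction: SD, power | ANCOVA: SD, power |
|---|---|---|
| 0.3 | 19.0, 79.5% | 15.3, 93% |
| 0.5 | 19.0, 79.5% | 16.5, 89% |
| 0.7 | 19.0, 79.5% | 17.5, 86% |

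If 19 U is the SD of a single score, the SD of change is 19 × √(2(1−r)) and the ANCOVA residual SD is 19 × √(1−r²):

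| r | Interaction: SD, power | ANCOVA: SD, power |
|---|---|---|
| 0.3 | 22.5, 65% | 18.1, 83% |
| 0.5 | 19.0, 79.5% | 16.5, 89% |
| 0.7 | 14.7, 95% | 13.6, 97% |

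**The case against.** The strongest reply is that sections 14 and 20 agree with each other. The trial is sized on a difference in change, the analysis estimates a difference in change, and 70 per group reproduces. The estimator is valid under randomisation and does use baseline, by subtraction, so the label could be called loose and not false. All of that stands. What it leaves untouched is the precision given up and the impression that the result conditions on baseline.

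Two stronger readings are tempting, and the documents support neither.
- A reader might infer that the interaction is biased. It is not: the displacement in step 3 is conditional on the imbalance observed and averages out over randomisations.
- A reader might infer that the trial is underpowered. The 65% figure needs 19 U to be a single-score SD and r to be as low as 0.3. Section 14 speaks of change, and on the single-score reading the interaction still reaches 79.5% at r = 0.5 and 95% at r = 0.7.

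It can also be said that this is secondary to a larger gap. The SAQ is not scheduled at baseline and section 20 models 6 months, so neither analysis can be computed as written for the 12-month endpoint. That is correct, and it must be repaired first. Adding a baseline SAQ and changing 6 months to 12 would still leave a change-score contrast under the same label.

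**Conclusion.** The point holds as a correction of labelling and efficiency. It does not show an invalid analysis or a failed sample size. With complete pairs the stated effect is the unadjusted difference in mean change, and with some follow-up missing it is close to that. On the natural reading of section 14, the planned analysis delivers its stated power, and conditioning on baseline would raise 79.5% to between about 86% and 93% for r between 0.7 and 0.3.

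The size of the gain rests on equal variances at the two times and on an assumed r, and cannot be fixed from the documents. It shrinks as r rises and vanishes only as the slope of follow-up on baseline approaches 1. It is a free improvement, conditional on a baseline SAQ being recorded.

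**What to change.** After a pre-randomisation SAQ has been added to the schedule and the model aligned to the 12-month endpoint, replace the sentence on the interaction in section 20 with: *The primary effect is the between-group difference in 12-month SAQ from a linear model with baseline SAQ as covariate.*

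If a repeated-measures form is preferred, use a two-time-point model with a common baseline mean for both arms and an unstructured covariance, and report the group difference at 12 months. This is close to ANCOVA, though not identical. Dropping the group term while keeping only a random patient intercept is not a substitute, because that forces equal variances at the two times.

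Use the same form for other continuous outcomes that have a baseline value. State in section 14 whether 19 U is the SD of change or of a single score. If the sponsor prefers to keep the interaction, call it the difference in mean change.

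Cost: wording in sections 14 and 20, with no added patients or visits. The baseline questionnaire is a separate requirement, already implied by section 14 (change) and section 20 (baseline). Consent precedes angiography and randomisation follows it at once in an open-label trial, so the questionnaire has to be fitted in between them.

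### Section 20 gives no usable analysis and no multiplicity control for the 11-biomarker endpoint; at an uncorrected 0.05 the chance of a false marker is about 43%, and up to 82–90% if tested per cause (independent tests, no true association)

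*Combined protocol and SAP*

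**What the plan says.** **Endpoint.** Section 12 lists as a secondary endpoint "Ability of different circulating biomarkers (ET-1, NPY, CRP, sCD40L and miRNA", followed by seven named microRNAs. That is four proteins or peptides plus seven microRNAs, 11 markers in all, to be assessed as diagnostic and stratification tools for individual causes. Sections 7 and 15 add prognosis and response to therapy. Section 6.b names the causes: plaque rupture or erosion, epicardial spasm, microvascular spasm and coronary embolism.

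**Data.** Sections 11a and 13 list the research blood sample under the precision arm only. Section 33 describes one draw around the index angiogram, with the proteins measured at baseline and the microRNAs on the same samples, in both serum and PBMC. CRP is an exception: it is also in the general T0 laboratory list, which the schedule shows under the standard arm. OCT, acetylcholine testing and transesophageal or contrast echocardiography are listed for the precision arm only.

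**Analysis.** Section 20 states: "Continuous outcome measures recorded at baseline and 6 months will be compared between randomized groups using a mixed effects linear regression model". Categorical outcomes get Fisher exact tests, again between randomized groups. The significance rule is general: "We will perform 2-tailed analysis and considered a p value" of at most 0.05 to be significant. Section 20 mentions no comparison between causes, no accuracy measure, no cut-off, no validation and no multiplicity adjustment.

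**The concern.** Whether a marker identifies a cause is a question about patients whose cause has been established, comparing those with that cause and those without it. Neither stated method asks it. An analyst who follows Section 20 literally cannot address the endpoint. One who improvises may choose the contrasts after seeing the data, with an uncorrected 0.05 as the only threshold in the plan.

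What is at stake is the credibility of any marker that the trial puts forward as a diagnostic tool, drawn from about 90 patients divided among several causes.

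**Working it through.** **1. The plan's own calculation.** The only computed figure is in Section 14, for the primary endpoint: "to detect a mean group difference of change in SAQ score of 9 U", with an SD of 19, 80% power and two-sided 5%.

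n per group = 2 × (1.960 + 0.842)² × 19² / 9² = 2 × 7.849 × 361 / 81 = 69.96, so 70.

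This reproduces the stated 70 per group (140 in total). It concerns the SAQ only; no sample size or error rate is given for the biomarkers. With 180 patients allocated 1:1, the precision arm has about 180 / 2 = 90.

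**2. Do the stated methods fit?**

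| Requirement of the Section 20 method | What the biomarker endpoint supplies |
|---|---|
| Values in both randomized arms | Research panel in the precision arm only; CRP alone is also measured in the standard arm |
| Mixed model: baseline and a follow-up value | One baseline sample |
| Fisher test: categorical outcome compared by arm | Marker levels, to be related to cause rather than arm |

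Having CRP in both arms does not help. The cause-defining tests are done in one arm, and a between-arm difference in CRP says nothing about diagnosing a cause.

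**3. Error rate if the general 0.05 rule is applied.** For m independent tests with no true association, P(at least one false positive) = 1 − 0.95^m, and the expected number is 0.05 × m.

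| Test structure (assumed) | m | P(at least one) | Expected |
|---|---|---|---|
| One test per marker | 11 | 1 − 0.5688 = 43.1% | 0.55 |
| Each marker against 3 causes (spasm types pooled) | 33 | 1 − 0.1840 = 81.6% | 1.65 |
| Each marker against 4 causes | 44 | 1 − 0.1047 = 89.5% | 2.2 |

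Even odds require ln 0.5 / ln 0.95 = 13.5, that is 14 independent tests.

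**4. Relaxing independence.** A simulation under no true association used 11 equally correlated markers, 90 patients and 2,000 replicates per setting. The group sizes and correlations are assumptions; the documents give neither.

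| Between-marker correlation | 0 | 0.3 | 0.5 | 0.7 | 0.9 |
|---|---|---|---|---|---|
| One overall test per marker, 3 causes (30/30/30) | 43% | 35% | 31% | 23% | 14% |
| Each cause versus the rest, 3 causes (30/30/30) | 76% | 69% | 58% | 44% | 29% |
| Each cause versus the rest, 4 causes (30/25/25/10) | 87% | 80% | 73% | 57% | 39% |

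Even with uncorrelated markers the per-cause figures fall below 82% and 90%, because contrasts of the same marker share patients.

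**5. Relaxing the global null.** If half the tests concern real associations, 1 − 0.95^(m/2) gives 24.6%, 57.1% and 67.6% for m = 11, 33 and 44 (independent tests).

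**6. What the rationale supports.** Sections 6.b and 6.c tie each measured marker to a mechanism: ET-1 and NPY to spasm (2); miR-16 and miR-26a to microvascular spasm (2); miR-145 and miR-222 to epicardial spasm (2); CRP, sCD40L, miR-155-5p, miR-483-5p and miR-451a to plaque rupture (5). That is 2 + 2 + 2 + 5 = 11 contrasts. None is tied to embolism.

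**The case against.** The strongest reply is that the error rates are hypothetical. Section 20 never says that 0.05 is the criterion for declaring a marker, and it names no biomarker test. This stands. Applying the general rule to the markers is an inference, and the firmer finding is that the analysis is missing.

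A reader might go further and infer that a false diagnostic marker is the likely outcome. The documents do not support that. One test per marker gives 43%, below even odds. The 33- and 44-test grids appear nowhere in the plan. The markers were chosen because of earlier reported associations, so a global null is itself an assumption, and correlation lowers the figures further. Nor is it accurate to say that every marker exists in one arm only, given routine CRP.

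The consequences are also limited. The endpoint is secondary, the abstract says only that markers may serve as diagnostic tools, and targeted treatment in Section 11a follows plaque, spasm or embolism findings rather than marker values.

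Finally, single-marker AUCs are one choice among several. Section 7 speaks of a marker profile, and Section 6.c of a microRNA signature for microvascular spasm (which includes miR-1 and miR-133, not in the measured panel). An AUC also needs a reference label, and OCT is done only when rupture or erosion is suspected. These points do not remove the gap, but the fix has to deal with them.

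**Conclusion.** The point holds as a gap in the analysis plan, of minor severity. Section 20 cannot answer the biomarker endpoint as written, and the endpoint has no multiplicity control and no exploratory label.

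The possible size is about 43% for at least one false marker with one test per marker, rising to at most 82–90% with per-cause testing. Both rest on independent tests, no true association and a test structure that the plan leaves undefined. Under the assumptions tried in steps 4 and 5, the range runs from 14% to 87%. The counts leave out prognosis, treatment response and the duplicate serum and PBMC measurements, each of which would add tests. The type I error of the primary SAQ comparison is not touched.

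**What to change.** Add a biomarker subsection to Section 20, restricted to the precision arm:

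- Pre-specify one contrast per marker: ET-1 and NPY for spasm; miR-16 and miR-26a for microvascular spasm; miR-145 and miR-222 for epicardial spasm; CRP, sCD40L, miR-155-5p, miR-483-5p and miR-451a for plaque rupture.
- Report the AUC with 95% CI for each, and control the false discovery rate at 5% (Benjamini-Hochberg) over these 11 tests.
- Name the microRNA source, serum or PBMC, used for these tests.
- State how patients without OCT, with no identified cause, or with several causes are classified. The OCT rule matters for the five plaque-rupture contrasts, where the label is not verified in every patient.
- Label as exploratory all other marker–cause pairs, multi-marker profiles, and the prognosis and treatment-response analyses.

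This needs no new patients, visits or samples. The cost is SAP text, some thought about the classification rules, and somewhat less power for each marker: the smallest of the 11 p-values is compared with 0.05 / 11 = 0.0045 and the largest with 0.05. In return, if no marker is truly associated and the tests are independent, the chance of any false claim among the 11 falls from 43% to 5%.
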